##### **4.3.1.1. Sensitivity Analyses of the Primary Efficacy Endpoint**

The following sensitivity analyses are planned to show the robustness of the primary analysis:

- 1) The primary analysis will be repeated using the PPS population (using an ANCOVA model and the same MCMC multiple imputation method).

- 2) The primary efficacy endpoint will be analyzed using a non-parametric Wilcoxon Rank Sum test using both the FAS and the PPS. Missing data will be handled using the same MCMC multiple imputation method as the primary analysis. The treatment effect will be estimated using the Hodges-Lehmann estimator of the location shift between ISIS 681257 treatment groups and the pooled placebo group. Asymptotic 95% CI and corresponding p-value will be provided.
- 3) The primary analysis will be repeated on the set of patients with non-missing Lp(a) values at the primary analysis time point using the FAS and the PPS.
- 4) Using controlled imputations (pattern mixture models [PMM] with ANCOVA) will be conducted to assess the robustness of the missing at random assumption. With this approach, missing not at random (MNAR) is assumed, and the mean function for the missing data from patients treated with ISIS 651257 who discontinue the study is pre-specified. Missing Lp(a) for placebo patients will be imputed using the same MCMC multiple imputation method as the primary analysis. Patients treated with ISIS 681257 who discontinue the study due to AE or lack of efficacy will have their post-discontinuation Lp(a) values imputed using estimates from the placebo patients using the copy increment from reference (CIR) approach, detailed in ([Carpenter et al. 2013](#)). The assumption is based on the fact that when a patient discontinues treatment due to informative missing data, at the time of discontinuation they would progress in a similar manner as placebo-treated patients. Otherwise, non-informative missing data will be imputed using the same MCMC method as the primary analysis, since it is assumed that those patients would have continued in a similar manner to similar patients in their own treatment group who remained on the study. Therefore, the missing data for these patients is expected to be missing at random.

#### 4.3.2. Analysis of the Secondary Efficacy Endpoints

##### 4.3.2.1. Percent Change from Baseline in fasting LDL-C

The percent change from baseline at the primary analysis time point in fasting LDL-C will be compared between each ISIS 681257 treatment groups and the pooled placebo group using an ANCOVA model with treatment groups as factors and log-transformed baseline LDL-C values as covariate. Similar to the primary endpoint, the ANCOVA model will use  $\log(Y/X)$  as dependent variable, where Y is the post-baseline value of LDL-C and X is the baseline value of LDL-C. Corresponding 95% CIs and p-value will be provided.

Mean (SD) percent change over time in fasting LDL-C will be plotted by ISIS 681257 treatment group and pooled placebo group, until there are fewer than 10% of the FAS/PPS population at a given visit. Waterfall plots of by-patient percent changes from baseline to the primary analysis time point will also be provided.

##### 4.3.2.2. Responder-Type Analysis

The proportion of patients who achieve:

- $\leq 125$  nmol/L ( $\leq 50$  mg/dL) in fasting Lp(a), or
- $\leq 75$  nmol/L ( $\leq 30$  mg/dL) in fasting Lp(a)

at the primary analysis time point will be compared between each ISIS 681257 treatment group and the pooled placebo group using a logistic regression model with log-transformed baseline Lp(a) as a covariate.

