**Table 1: Study Drug Dosing Information**

Cohort	Treatment	Volume to Administer/Dose	# Doses	Total ISIS 681257
A	20 mg ISIS 651257 or placebo (every 4 weeks)	0.2 mL	≤ 13	≤ 260 mg
B	40 mg ISIS 651257 or placebo (every 4 weeks)	0.4 mL	≤ 13	≤ 520 mg
C	60 mg ISIS 651257 or placebo (every 4 weeks)	0.6 mL	≤ 13	≤ 780 mg
D	20 mg ISIS 651257 or placebo (every 2 weeks)	0.2 mL	≤ 26	≤ 520 mg
E	20 mg ISIS 651257 or placebo (every week)	0.2 mL	≤ 52	≤ 1040 mg

The treatment portion of the study will be complete when the last enrolled patient reaches 6 months of exposure. All patients still on treatment will have their last dose taken as scheduled, and they will enter a 16-week post-treatment follow-up period at one dosing interval post last dose. Accordingly, for each treatment cohort treatment period is defined as the time from the first dose through one dosing interval post last dose.

Patients  $\geq 18$  and  $\leq 80$  years old with elevated plasma Lp(a) levels ( $\geq 60$  mg/dL ) and a clinical diagnosis of CVD are eligible for enrollment upon meeting the study specific eligibility criteria. Patients will be on standard-of-care preventative therapy for other than elevated Lp(a) CVD risk factors as per current guidelines.

Clinical diagnosis of CVD is defined as documented CAD, stroke, or PAD. A diagnosis of CAD has to be documented by any of the following:

- Angiographic evidence of  $\geq 50\%$  stenosis of 1 or more major epicardial coronary arteries.

- History of myocardial infarction documented by positive enzymes, and either symptoms of myocardial ischemia, or electrocardiogram (ECG) changes (Thygesen et al. 2012).
- History of coronary revascularization.
- Evidence of cardiac ischemia on exercise testing, or imaging study.

Patients will be evaluated for study eligibility during Screening, which takes place within 4 weeks prior to Day 1 (the first day of Study Drug administration). Patients who are determined to be eligible, based on screening assessments, will be enrolled in the study at Day 1 and randomly assigned to 1 of the 5 parallel dosing cohorts, with each cohort having a 5:1 ratio to receive ISIS 681257 or matching volume of placebo, respectively, by SC injection for up to 52 weeks.

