##### 1.2.5.2. Secondary Efficacy Parameters

The secondary endpoints include the following parameters from baseline at the primary analysis time point for ISIS 681257 compared to placebo:

- Percent change from baseline in LDL-C.
- Proportion of patients who achieve plasma Lp(a)  $\leq 125$  nmol/L ( $\leq 50$  mg/dL).
- Proportion of patients who achieve plasma Lp(a)  $\leq 75$  nmol/L ( $\leq 30$  mg/dL)
- Percent change from baseline in apoB.
- Percent change from baseline in OxPL-apo(a).
- Percent change from baseline in OxPL-apoB.

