### **3. GENERAL STATISTICAL METHODS**

#### **3.1. Sample Size Justification**

Based upon prior clinical trial experience with ISIS 681257, it is estimated that the standard deviation (SD) of the percent change in Lp(a) is approximately 20%. With 23 patients in each ISIS 681257 treatment group and 23 in placebo group there would be approximately 90% power to detect a 20% difference in percent change in Lp(a) levels between the ISIS 681257 treatment groups and placebo group at an alpha level of 0.05, assuming 30% reduction in the ISIS 681257 patients and 10% reduction in the placebo patients.

Based upon prior clinical trial experience with Ionis ASOs, assuming the incidence rate of platelet count below LLN in placebo-treated patients is 1.9%, in the ISIS 681257-treated patients is 3.8%, twice the incidence rate observed in placebo, with 45 patients in each ISIS 681257 treatment group, there would be approximately 80% probability of observing at least 1 event.

Therefore, approximately 270 patients (54 patients per cohort, including 45 patients per cohort treated with ISIS 681257), will be randomized to ensure that both the safety and efficacy of ISIS 681257 will be adequately characterized in the study.

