### **4.3. Efficacy Evaluation**

All efficacy analyses related to Lp(a) will be primarily performed, and the actual changes in Lp(a) will be presented in nanomoles per liter (nmol/L) because the direct output of the Lp(a) assay used in this study is provided in molar units. Due to high degree of size heterogeneity of apo(a) protein, use of molar concentrations is considered highly preferable over use of mass concentrations (mg/dL) (Markovina SM and Albers JJ, 2016). For completeness, the actual Lp(a) results will also be presented in mg/dL using conversion factor of 2.5. Although the conversion factor for transforming Lp(a) values from nmol/L to mg/dL highly varies due to variability of mass of nonprotein components of Lp(a), it is accepted in the literature that Lp(a) in nmol/L is approximately 2.4-2.5 fold higher than Lp(a) in mg/dL (Tsimikas S et al 2015, Viney et al, 2016).

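### On the SAP's planning figures the Lp(a) ≤ 75 nmol/L responder analysis will more likely than not have no placebo responders, and Section 4.3.2.2 has no rule for that case

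*SAP*

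**What the plan says.** SAP Section 1.2.5.2 lists two responder endpoints. The stricter one is "Proportion of patients who achieve plasma Lp(a) $\leq 75$ nmol/L ( $\leq 30$ mg/dL"); the other is 125 nmol/L (50 mg/dL). Section 4.3.2.2 compares each of the five dose groups with pooled placebo on both thresholds "using a logistic regression model with log-transformed baseline Lp(a) as a covariate". It does not say whether inference is Wald, likelihood-ratio, score, exact or penalised, and it gives no fallback for a group with no responders.

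The inputs that decide how many placebo responders to expect are elsewhere in the SAP:

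- Section 1.2.1 admits patients with "elevated plasma Lp(a) levels ( $\geq 60$ mg/dL").
- Section 4.3 has results "presented in mg/dL using conversion factor of 2.5", so the entry floor is about 150 nmol/L.
- Section 3.1 states "standard deviation (SD) of the percent change in Lp(a) is approximately 20" per cent, "assuming 30% reduction in the ISIS 681257 patients and 10% reduction in the placebo patients".
- Section 3.1 plans 54 patients per cohort, 45 of them on active drug. Section 3.5 pools the placebo patients.

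Section 4.3.2.3 sends missing secondary data to the imputation method of Section 3.10.1.

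**The concern.** A placebo patient at the entry floor must lose half of baseline Lp(a) to count as a responder at 75 nmol/L, and a patient with a higher baseline must lose more. The planning figures put such a fall two or more standard deviations from the placebo mean, so an empty placebo group is a realistic outcome.

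Pooled placebo is the shared reference for all five comparisons. If it has no responders, the likelihood keeps rising as the placebo log-odds goes to minus infinity. The maximum-likelihood odds ratio is then infinite for every dose that has responders, and the reported standard error only reflects where the iterations stopped. A Wald p-value from that fit sits near 1 however strong the drug effect.

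At stake is a named secondary endpoint without a usable effect estimate or interval, and a method chosen after the empty cell has been seen in unblinded data.

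**Working it through.** **Planning figure first.** Section 3.1 states "With 23 patients in each ISIS 681257 treatment group and 23 in placebo group there would be approximately 90% power". The standardised difference is 20/20 = 1 and the noncentrality is √(23/2) = 3.39. A two-sided 5% t-test with 44 df has 91.2% power (92.4% by the normal approximation). The stated figure is reproduced, so the mean and SD are read as intended. The SAP states no expected responder rate.

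**Placebo numbers.** 54 − 45 = 9 per cohort, and 5 × 9 = 45 pooled.

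**Chance of an empty placebo group at 30 mg/dL (75 nmol/L).** For baseline b in mg/dL, with percent change taken as normal:

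p = Φ( [ (30/b − 1) × 100 + 10 ] / 20 ), and P(none) = (1 − p)^45.

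| All baselines at (mg/dL) | Fall needed | p | Expected responders of 45 | P(none) |
|---|---|---|---|---|
| 60 | 50.0% | 2.28% | 1.02 | 36% |
| 65 | 53.8% | 1.42% | 0.64 | 53% |
| 70 | 57.1% | 0.92% | 0.41 | 66% |
| 80 | 62.5% | 0.43% | 0.19 | 82% |
| 100 | 70.0% | 0.13% | 0.06 | 94% |

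Real baselines will be spread out. As an assumption, let log(baseline/150 nmol/L) be exponential and average p over it:

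| Assumed median, nmol/L (mg/dL) | Expected responders at 75 nmol/L | P(none) |
|---|---|---|
| 165 (66) | 0.57 | 56% |
| 200 (80) | 0.30 | 74% |
| 275 (110) | 0.17 | 84% |

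Two variations raise these figures. A placebo mean change of 0 gives 87–96%. A log-normal ratio with mean 0.9 and SD 0.2 gives 92–98% (79% with every baseline at the floor). A larger SD or a larger placebo fall would lower them.

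**The 125 nmol/L endpoint.** The same spreads give 10.0 to 3.1 expected placebo responders and P(none) of about 0–4%.

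**What happens with 0/45 on placebo.** In a simulation of 45 v 45 with the log-baseline covariate (400 runs per scenario), among runs with no placebo responders:

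- The Wald test rejected in 0% of runs.
- The likelihood-ratio test from the same model rejected in about 100% of runs when the active mean fall was 50–80%.
- The likelihood-ratio test rejected in about 39–53% of runs at the planned 30% fall.

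Unadjusted 2 × 2 results show the size. The likelihood-ratio statistic for k/45 v 0/45 is twice the difference between the separate-rates and common-rate log-likelihoods. For k = 5 it is 2 × (−15.697 + 19.310) = 7.23, p = 0.007. In this saturated case the Firth odds ratio adds 0.5 to each cell. For k = 9 it is (9.5 × 45.5)/(36.5 × 0.5) = 23.7. The Firth intervals profile the log-likelihood plus ½ log{45p₀(1 − p₀) × 45p₁(1 − p₁)}, cut at a fall of 3.84/2.

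| Active v placebo | ML odds ratio | Likelihood-ratio p | Fisher p | Firth odds ratio (95% profile interval) | Firth p |
|---|---|---|---|---|---|
| 5/45 v 0/45 | infinite | 0.007 | 0.056 | 12.4 (1.3 to 1,640) | 0.023 |
| 9/45 v 0/45 | infinite | 0.0002 | 0.0025 | 23.7 (2.8 to 3,090) | 0.001 |
| 27/45 v 0/45 | infinite | 2 × 10⁻¹² | 5 × 10⁻¹¹ | 135 (17 to 17,470) | 1 × 10⁻¹¹ |

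At 5/45 the valid tests fall on different sides of 0.05, so it matters that the choice is made in advance.

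**Imputation.** Section 3.10.1 ends by giving patients with a missing endpoint the median of their imputed values, which leaves one dataset. Section 4.3.1 fits 100 models and combines them for the primary endpoint. Section 4.3.2.3 points the secondary endpoints to Section 3.10.1 only. If 100 fits are to be combined, each needs a finite estimate and standard error, and a separated fit gives neither.

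**The case against.** **The doses can still be tested.** A reader might infer that an empty placebo group makes every comparison untestable. The SAP does not support that. Separation defeats the estimate and the Wald test, while a likelihood-ratio or exact test remains valid and is powerful at moderate response rates. This objection stands in full. It does not supply a finite odds ratio, and the SAP names no such test.

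**The SAP does not commit to Wald inference.** This is correct. It specifies only a logistic regression, so the fault is an unspecified test and interval rather than a prescribed method that fails.

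**The probability depends on baselines the SAP does not give.** This also stands. The range starts at 36%. Section 3.4 takes baseline from Day 1 or the nearest pre-dose value, while eligibility is judged at screening, so a Day 1 value under 60 mg/dL is possible and the 50% fall is not a strict minimum. An imputed value could also create a placebo responder.

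**Pooling over imputations makes it worse.** A reader might infer this too. It holds only if the Section 4.3.1 combination applies. Under the median-value rule in Section 3.10.1 there is nothing to pool.

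**The consequence is limited.** This is agreed. Section 3.7 has no testing procedure that depends on this p-value, counts and percentages will be shown anyway, and the 125 nmol/L comparison is largely unaffected.

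**Conclusion.** The point holds for the 75 nmol/L endpoint. On the SAP's placebo mean and SD with 45 pooled placebo patients, an empty reference group is more likely than not unless nearly all baselines sit at the entry floor: 36% with all at 60 mg/dL, and about 56–84% for assumed skewed baselines above it. These figures rest on normally distributed percent changes and on an assumed baseline spread. If the group is empty, maximum-likelihood logistic regression gives no finite odds ratio, and no usable Wald interval or p-value, for any dose with responders. The SAP should be changed before unblinding, but this is a gap in one secondary analysis. The primary ANCOVA is not touched.

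**What to change.** In Section 4.3.2.2, prespecify Firth-penalised logistic regression for the 75 nmol/L endpoint, with treatment group and the same log-baseline covariate, and with profile penalised-likelihood 95% confidence intervals and p-values. It may be used at 125 nmol/L for consistency, although separation is unlikely there.

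In the same place, say how the result is obtained from the imputed data, and reconcile Sections 3.10.1 and 4.3.1. If the median imputed value is used, the model is fitted once. If 100 fits are combined, Firth log odds ratios and standard errors can be pooled by the rule used for the primary endpoint. Profile-likelihood limits and p-values do not combine by that rule, so the SAP must then say which interval and p-value are reported.

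The cost is a few sentences, one modelling option and slight shrinkage of the odds ratios. With an empty placebo group the upper confidence limit will still be very wide, so the lower limit and the p-value carry the information.

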#### 4.3.2.3. Percent Change from Baseline in Other Lipid Parameters

The percent change from baseline at the primary analysis time point in fasting apoB, OxPL-apo(a), and OxPL-apoB will be compared between each ISIS 681257 treatment groups and the pooled placebo group using an ANCOVA model with treatment groups as factors and the respective log-transformed baseline lipid parameter values as covariate. Similar to the primary endpoint, the ANCOVA model will use  $\log(Y/X)$  as dependent variable, where Y and X are the post-baseline values and the baseline value of the lipid parameter being analyzed, respectively. Corresponding 95% CIs and p-value will be provided.

Mean (SD) percent change over time, until there are fewer than 10% of the FAS/PPS population at a given visit, in these fasting lipid parameters will be plotted by ISIS 681257 treatment group and pooled placebo group. Waterfall plots of by-patient percent changes from baseline to the primary analysis time point will also be provided.

All analyses of secondary endpoints will be performed using the FAS as primary and the PPS as supportive. Patients with missing data for any secondary endpoints will have their respective parameter values (LDL-C, Lp(a), apoB, OxPL-apo(a), and OxPL-apoB) imputed using the imputation method described in [Section 3.10.1](#).

All secondary endpoint data will be provided in data listings.

#### 4.3.3. Supportive Efficacy Analysis

Supportive efficacy analyses will be conducted on data collected beyond the primary analysis time point. Log-transformed ratio of post-baseline to baseline will be analyzed for the primary endpoint using a Mixed Model of Repeated Measurements (MMRM). Treatment group and visit will be fitted as factors and log transformed baseline will be fitted as a continuous covariate. Treatment group by visit and visit by baseline will be included as interaction terms in the model. A term for visit will be included in the repeated statement (in SAS PROC MIXED) and an unstructured correlation matrix will be used thus allowing adjustment for correlations between time points within subjects. The Kenward-Roger adjustment for degrees of freedom will be used.

Since not all patients will have the same duration on-treatment, the number of patients at each visit after the primary analysis time point will be different. The supportive efficacy analyses will include the changes (summary statistics only) and percent changes from baseline of Lp(a), LDL-C, apoB, OxPL-apo(a), and OxPL-apoB at each subsequent visit after the primary analysis time point. The supportive analysis of percent changes will be modeled in a similar way as the supportive primary efficacy analysis. Visits will be presented until there are fewer than 10% of the FAS/PPS.

Mean (SD) percent changes over time in all parameters above will be plotted by ISIS 681257 treatment group and pooled placebo group.

Supportive efficacy analyses will be performed using the FAS and the PPS.

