## 1.2. Study Design

### 1.2.1. Synopsis of Study Design

This is a multicenter, randomized, double-blind, placebo-controlled, dose-ranging study. ISIS 681257 (or placebo) will be administered subcutaneously (SC) every week, every 2 weeks, or every 4 weeks, depending on cohort assignment, for up to 52 weekly doses, up to 26 every 2-week doses, or up to 13 every 4-week doses. Minimum treatment duration is 6 months, maximum treatment duration is 12 months.

The primary analysis time point is at Week 25 for patients who received every 4-week dosing (Cohorts A-C) and at Week 27 for patients who received 2-week or weekly dosing (Cohorts D and E). For patients continuing treatment beyond the primary analysis time point additional supportive efficacy analysis (to evaluate whether the treatment effect is maintained) and safety analysis (for the purpose of dose(s) selection) will be repeated at the completion of Study Drug treatment. A description of each cohort is presented in [Table 1](#).

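### The supportive MMRM (SAP 4.3.3) is labelled an FAS analysis, but its stated input is data after Week 25/27, which leaves out earlier dropouts and all earlier on-treatment values

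*SAP*

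**What the plan says.** Section 4.3.3 opens with the data: "Supportive efficacy analyses will be conducted on data collected beyond the primary analysis time point". It then gives the model: "Log-transformed ratio of post-baseline to baseline will be analyzed for the primary endpoint using a Mixed Model of Repeated Measurements (MMRM". Treatment group, visit, log baseline, and the treatment-by-visit and visit-by-baseline interactions are fitted, and "an unstructured correlation matrix will be used thus allowing adjustment for correlations between time points within subjects". Results for Lp(a), LDL-C, apoB, OxPL-apo(a) and OxPL-apoB are given "at each subsequent visit after the primary analysis time point", and for these parameters "The supportive analysis of percent changes will be modeled in a similar way as the supportive primary efficacy analysis". The section ends: "Supportive efficacy analyses will be performed using the FAS and the PPS".

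Section 1.2.1 gives the purpose: "For patients continuing treatment beyond the primary analysis time point additional supportive efficacy analysis (to evaluate whether the treatment effect is maintained".

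No sentence brings post-baseline visits before the primary time point into this model, and no imputation is stated for it. The primary analysis differs. Sections 3.10.1 and 4.3.1 impute missing Lp(a) from baseline and post-baseline values, on the reasoning that missingness may be related to observed data.

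**The concern.** A likelihood-based repeated-measures model handles missing data under missing at random by conditioning on the values it is given. If the values that predict dropout are withheld, that protection is lost. A programmer following section 4.3.3 would keep only records after Week 25/27. Two things follow:

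- A patient who left before then has no record in the fit. The FAS (section 2.1: randomized and dosed at least once) is then the analysis set in name only.
- For those patients, the model in effect assumes that absence depends on treatment and baseline only, although their on-treatment Lp(a) was measured.

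This sits badly with the rest of the SAP. Section 3.10.1 relies on exactly those earlier values, and the pattern-mixture analysis in section 4.3.1.1 treats discontinuation for adverse events or lack of efficacy as informative.

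At stake is the reading of maintenance. The Week 25/27 estimate describes the imputed FAS, while later estimates would describe those who reached later visits. A difference between the two mixes change over time with change of population.

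**Working it through.** The SAP states no figure for this model, so the check is an illustration that uses the SAP's planning values where they exist.

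**Inputs from the SAP (section 3.1).** Reductions of 30% v 10%; SD of percent change about 20%; 45 active patients per cohort; 270 − 5 × 45 = 45 pooled placebo. The planning inputs reproduce: 23 v 23, difference 20, SD 20, two-sided 0.05 gives 91.2% power by the t-test, against about 90% stated. That figure has no bearing on the present point.

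**Assumptions (not in the SAP).**
- Log-scale SD 0.29 in both arms, suggested by 0.20/0.70 = 0.286.
- Correlation ρ of 0.5 or 0.8 between an early on-treatment visit and a late visit.
- Dropout before the primary time point of 5%, 10% or 20% per arm. In the active arm its log-odds rise by 0, 1 or 2 per SD of early Lp(a), so poorer responders leave. In placebo it is unrelated to response.
- A further 40% lost at late visits because treatment ends administratively, unrelated to response.

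**True contrast.** log(0.70/0.90) = −0.251, a 22.2% relative reduction.

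**Late-only bias.** Bias = ρ × SD × (mean early z-score of those retained). For ρ = 0.8, 20% dropout and log-odds 2 per SD, the retained active patients have mean z = −0.262, so bias = 0.8 × 0.29 × (−0.262) = −0.061.

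**Realistic late-visit standard error.** Patients left per arm: 45 × 0.60 × 0.80 = 21.6, so SE = 0.29 × √(2/21.6) = 0.088. With all 45 per arm it would be 0.29 × √(2/45) = 0.061, which is too small for a late visit.

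**Simulation** (3,000 trials per setting). Late-only means are compared with maximum likelihood that keeps the early visit:

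| ρ | Dropout | Log-odds per SD | Bias, late only | Bias, early visit kept | SE, late only | Size of bias/SE | Late-only reduction (true 22.2%) |
|---|---|---|---|---|---|---|---|
| 0.5 | 5% | 1 | −0.0064 | +0.0006 | 0.0815 | 0.08 | 22.7% |
| 0.8 | 10% | 1 | −0.0202 | +0.0011 | 0.0830 | 0.24 | 23.8% |
| 0.5 | 20% | 2 | −0.0389 | −0.0013 | 0.0864 | 0.45 | 25.2% |
| 0.8 | 20% | 1 | −0.0405 | +0.0001 | 0.0872 | 0.46 | 25.3% |
| 0.8 | 20% | 2 | −0.0591 | +0.0014 | 0.0875 | 0.68 | 26.7% |
| 0.8 | 20% | 0 | −0.0006 | −0.0002 | 0.0899 | 0.01 | 22.3% |

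The last column is 1 − (0.70/0.90) × exp(bias); for the fifth row, 1 − 0.778 × exp(−0.0591) = 26.7%. Over all response-related settings the late-only bias runs from −0.006 to −0.059. Keeping the early visit leaves it within about 0.002 and usually lowers the SE (0.070 v 0.083 at ρ = 0.8 and 10% dropout). When dropout is unrelated to response, late-only bias is also within about 0.002. If better responders were the ones to leave, the sign in the formula reverses.

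**The case against.** **The target may be conditional.** Section 1.2.1 frames the analysis for patients who continue treatment. Against that question, leaving out earlier dropouts is the target and not a bias. This has force, but section 4.3.3 names the FAS and does not say the result is conditional on continuation. The two sections need reconciling.

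**The SAP does not say only.** The sentence on later visits may describe what is reported, and naming the FAS would fit a model using all visits. A reader might infer that the sponsor has definitely decided to discard the earlier visits; the text does not prove that intent. It does fix the input in its opening sentence, and nothing corrects it.

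**Late missingness does not rest on baseline alone.** That stronger reading is wrong for patients with some late visits: the unstructured model also conditions on the late values they have. It is right only for patients with no late record.

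**The mechanism is assumed.** The stopping rules named in section 1.2.3 concern liver, renal and platelet results, not Lp(a). Dropout for adverse events could select poorer responders, better responders or neither. This stands, and so neither direction nor size can be claimed from the SAP.

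**Little depends on it.** The analysis is supportive, and the primary analysis deals with earlier dropout by imputation, backed by a pattern-mixture sensitivity analysis. This stands and limits the weight of the point.

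**Conclusion.** The point holds as a mismatch between the FAS label and the restricted input, with a better method available from post-baseline Lp(a) data that the SAP already uses for imputation. Followed literally, section 4.3.3 gives late contrasts in a selected group if early dropout is related to Lp(a) response, and these contrasts are not comparable with the Week 25/27 FAS estimate.

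Under the stated assumptions the bias is about 0.01 to 0.06 log units, about 0.1 to 0.7 of a late-visit standard error. At most, a true 22.2% relative reduction reads as 26.7%. Dropout rate, mechanism and correlation are all assumed, and the illustration uses one early and one late visit without the baseline covariate.

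A reader might infer that the late results will overstate maintenance, or that the bias could exceed one standard error. The SAP supports neither: direction depends on who leaves, and ratios above one arise only from heavier assumed dropout set against a standard error that ignores patients lost by the late visits. Administrative end of treatment is not itself a source of bias here. The primary inference is unaffected.

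**What to change.** In section 4.3.3, state that the model is fitted to all FAS patients using the scheduled post-baseline visits: at least the combined Week 25/27 visit and several earlier visits common to the cohorts. Report estimates and contrasts v pooled placebo only at visits after the primary time point. Apply the same rule to LDL-C, apoB, OxPL-apo(a) and OxPL-apoB.

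If an analysis of continuing patients is also wanted, as section 1.2.1 suggests, describe it as conditional on continuation and do not call it FAS.

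The cost is a short text change, a larger unstructured matrix (contained by using a subset of earlier visits), and a rule for mapping visits across dosing schedules.
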